NON-INTERVENTIONAL (NI) STUDY PROTOCOL

Study Information

Title	A standing cohort to understand the characteristics of patients with COVID-19 and contextualize the COVID-19 complication and safety events of interests using US OPTUM EHR data
Protocol number	C4671040
Protocol version identifier	3.0
Date	23 August 2022
EU Post Authorization Study (PAS) register number	EUPAS48654
Active substance	Nirmatrelvir/Ritonavir (ATC code J05AE30)
Medicinal product	Paxlovid
Research question and objectives	Research Questions: What are the demographic and clinical characteristics and healthcare utilization of all Coronavirus Disease 2019 (COVID-19) patients (ie, all patients with a diagnosis of COVID-19 in the Optum database (Overall Source Cohort); and multiple subcohorts including, COVID-19 patients with characteristics similar to the Paxlovid clinical trial programs (Trial Similar Cohorts) and COVID-19 patients treated with Paxlovid (Paxlovid Subcohort)? What is background incidence of clinical manifestations of COVID-19 among COVID-19 patients including subpopulation of interests (eg, hospitalized patients, trial similar patients)?

Pfizer Confidential

RedactedRedacted

RedactedRedactedRedactedRedactedRedactedRedacted
RedactedRedacted

RedactedRedactedRedactedRedactedRedacted

Version 3.0, Amendment 2, 23 August 2022

What are the background rates of events that may be potential Paxlovid safety concerns among COVID-19 patients?

What are the incidences of long COVID-19 or post-acute sequalae SARS CoV-2 (PASC) the characteristics of patients with long COVID?

What is the feasibility to assess the Realworld effectiveness of Paxlovid?

The following are the research objectives that will be addressed in this study:

Primary Objectives:

Objective 1: Describe the distribution of demographics, co-morbid conditions, medical history, selected biomarkers, and healthcare utilization at baseline for COVID-19 patients (including subpopulation with long COVID).

Objective 2: Describe the time to clinical events (eg, hospitalization, intensive care unit (ICU) admission, death).

Objective 3: Estimate background incidence of COVID-19 manifestations/complications and safety outcome of interests following COVID-19 infection or Paxlovid exposure.

Objective 4: Estimate incidence of long COVID-19 or PASC and assess health effects of Long COVID.

Objective 5: Describe the health equity and demographic and clinical characteristics (eg, co-morbid conditions, outcomes, treatment patterns, healthcare utilization) among patients treated with Paxlovid.

Secondary Objectives:

Objective 1: Estimate the incidence of oxygen supplementation among COVID-19

	patients hospitalized with mechanical ventilation/ECMO.
Author	Redacted Redacted Redacted Redacted Redacted Redacted
Co Author	Redacted Redacted Redacted Redacted Redacted Redacted

This document contains confidential information belonging to Pfizer. Except as otherwise agreed to in writing, by accepting or reviewing this document, you agree to hold this information in confidence and not copy or disclose it to others (except where required by applicable law) or use it for unauthorized purposes. In the event of any actual or suspected breach of this obligation, Pfizer must be promptly notified.

2. LIST OF ABBREVIATIONS

Abbreviation	Definition
AE	Adverse event
ARDS	Acute (or adult) respiratory distress syndrome
BMI	Body mass index
CABG	Coronary artery bypass graft
CI	Confidence interval
COPD	Chronic obstructive pulmonary disease
COVID-19	Coronavirus disease 2019
CRP	C-reactive protein
CVD	Cardiovascular disease
ER	Emergency room
EU	European Union
FDA	Food and Drug Administration
GPP	Good Pharmacoepidemiology Practice
HBV	Hepatitis B virus
HCV	Hepatitis C virus
HF	Heart Failure
HIPAA	Health Insurance Portability and Accountability Act
HIV	Human immunodeficiency virus
HMG-CoA	3-hydroxy-3-methylglutaryl co-enzyme A
ICD	International class disease
IEC	Independent Ethics Committee

Abbreviation	Definition
ILD	Interstitial lung disease
IRB	Institutional Review Board
LDH	Lactate dehydrogenase
NA	Not Applicable
NIH	National Institute of Health
NI	Non-interventional
PAH	Pulmonary arterial hypertension
PAS	Post-Authorization study
PASS	Post-Authorization Safety Study
PCR	Polymerase chain reaction
RWD	Real world data
SAP	Statistical Analysis Plan
SARS-CoV-2	Severe acute respiratory syndrome coronavirus 2
US	United States

4. ABSTRACT

In Annex 1 stand alone document.

5. AMENDMENTS AND UPDATES

Amendment number	Date	Protocol section(s) changed	Summary of amendment(s)	Reason
1 administrative	24 May 2022	Title Page and section 8	Added research question: What is the feasibility to assess the Real-world effectiveness of Paxlovid? Added Exploratory objective 3: Assess the feasibility of Real-world effectiveness of Paxlovid in reducing the COVID 19 related outcomes (eg, hospitalization).	Understanding Real-world effectiveness of Paxlovid can provide useful data to help expand the leaning from the previous clinical trials and accelerate on- going or future clinical trials
		Title page	Added PASS information to title page.	Study was evaluated as voluntary PASS study and wording had to be aligned with internal requirements.
		Section 7	Added mandatory PASS wording	Study was evaluated as voluntary PASS.
		Section 9.2.2.3	Added: Method to refine index date per research question will be defined in Statistical analysis plan (SAP)	To clarify the language of index date and follow up.
		Section 9.3	Added: Potential effectiveness of interests* • Hospitalization • All-cause mortality • ICU/Mechanical Ventilation • In Hospital death *The outcomes may be removed or added depending on the data availability for proper analyses.	These 4 outcomes were added, because they are severe COVID 19 outcomes aligned with Paxlovid indication
		Section 9.8	Added: To assess the feasibility of real-world effectiveness of Paxlovid, we will apply propensity score matching (PSM) method to control confounding and prescription time distribution method (PTDM) to handle immortal bias.	One of the challenges using real world data is to deal with confounding and bias. PSM and PTDM were selected to allow us better control confounding and cope with immortal bias

Amendment number	Date	Protocol section(s) changed	Summary of amendment(s)	Reason
2 substantial	23 Aug 2022	Title page	Corrected format and information on title page. Deleted Exploratory objectives.	To align with correct title page for PASS study conducted in USA. Title page should only show primary and secondary objectives.
		Section 3	Added "NIS Lead" to table.	To align with requirements, the role of "NIS Lead" was added to the table.
			Deleted table of Co-Investigators.	This table is for studies with study sites, which is not the case for this study.
		Section 4	Added section for abstract.	Since this is a PASS the protocol abstract is required.
		Section 5	Added new table for amendments and updates.	The correct table has been added to list all the amendments and updates.
		Section 6	Milestones were updated.	Update of milestones was done to align with current status.
		Section 9.1	Added that this is a secondary structured data collection.	For clarification the study type was added to this section.
		Section 9.2.1	Added a sentence describing what a validation substudy is.	This sentence was added for clarification.
		Section 9.3.1 and section 9.3.2	Rearranged inclusion and exclusion criteria:	Change was done to be aligned with template and facilitate understanding
		Section 9.4	Added clarification of COVID-19 Re- infection and Rebound	This sentence was added for clarification.
		Section 9.6	Added 2 sentences at the end of the section.	Text was added to describe new data source starting at the end of 2022.

Amendment number	Date	Protocol section(s) changed	Summary of amendment(s)	Reason
		Section 10.1	Deletion of second sentence in this section.	The deleted sentence was in the wrong section, it is part of section 11.
		Section 11	Changed text to align with correct safety wording.	This study does not have any unstructured data, safety wording was aligned.
		Section 12	Clarified that there will be one final study report and multiple publications.	There will be no interim report. Interim data analysis will be published as scientific manuscript.
		Section 14	Added section 14.	Section 14 was added to list the figures.
		Annex 1	Added table in annex 1.	Table in annex 1 was added because the stand alone abstract is required.
		Throughout the protocol	Minor editorial edits and correction of spelling mistakes.	NA

6. MILESTONES

Milestone	Planned date
Start of data collection	1 May 2022
Registration in the European Union (EU) PAS register	19 August 2022
End of data collection	28 February 2025
Final study report	30 January 2026

7. RATIONALE AND BACKGROUND

Background: A novel coronavirus, severe acute respiratory syndrome coronavirus 2 (SARS-CoV- 2), was first identified in December 2019 as the cause of a respiratory illness designated COVID-19.¹ The infection may be asymptomatic but symptomatic cases may present with cough, fever, dyspnea, headache, diarrhea, altered mental status, myalgia etc. Serious disease may manifest as acute respiratory distress syndrome, septic shock, and multi-organ dysfunction. As of January 2022, at least 324,196,758 cases have been confirmed worldwide, and at least 5,531,843 deaths have occurred.²

A number of different classes of drugs are being evaluated or newly developed for treatment or post-exposure prophylaxis of COVID-19. As of the date of issuance of clinical trial of Paxlovid (PF-07321332/ritonavir), only 1 anti-viral drug with activity against SARS-CoV-2, remdesivir, an Ribonucleic acid (RNA) polymerase inhibitor, has received approval in hospitalized patients with COVID-19³ Monoclonal antibodies (containing casirivimab and imdevimab or bamlanivimab and estesevimab) received emergency use authorization for mild to moderate COVID19 in recently diagnosed high risk nonhospitalized patients. Both of these options are administered intravenously and require administration by healthcare professionals. As of October 2021, there were no approved oral alternatives to PF-07321332/ritonavir for the treatment of mild-to-moderate COVID-19 in adult patients with positive results of direct SARS-CoV-2 viral testing, and who are at high risk for progression to severe COVID-19, including hospitalization or death. 4-6

There is an urgent and unmet need for antiviral agents that could be used for the treatment of non-hospitalized persons with COVID-19. Paxlovid, a potent and selective inhibitor of the SARS-CoV-2 3CL protease, was developed by Pfizer Inc. as an oral treatment in patients with COVID-19 in outpatient setting. The coronavirus 3CL protease is a virally encoded enzyme that is critical to the SARS-CoV-2 replication cycle, analogous to other obligatory virally encoded proteases (eg, human immunodeficiency virus (HIV) Protease, Hepatitis C virus (HCV) Protease) ⁷ In December 2021, Food and Drug Administration (FDA) has authorized the emergency use of Paxlovid in adult and pediatric patients 12 years of age and older (weighing at least 88 pounds (40 kg)]) with positive results of direct SARS-CoV-2 viral testing, and who are at high risk for progression to severe COVID-19, including hospitalization or death. ⁸

There is limited information about the safety and effectiveness of using Paxlovid, to treat people with mild-to-moderate COVID-19 in real-world setting. Understanding the epidemiology and clinical manifestations of COVID-19, as well as the background rates of potential Paxlovid related adverse events (AEs) among COVID-19 patients who are at high and standard risk of progression to severe illness in real world setting can provide critical context for interpreting potential safety events and clinical manifestations in on-going clinical trials post-marketing, with broaden patient population. This population based cohort study using United States (US) OPTUM COVID-19 EHR data will provide background rates of safety events of interest to support Paxlovid program. The Phase 3 clinical trial inclusion and exclusion criteria will be applied to a subgroup of the population to create a trial similar cohort. This study is being conducted in anticipation of the need to address possible questions about safety emanating from reports of AEs associated with the Paxlovid. The timeframes for this study will consider the health impacts as well as changes in healthcare utilization that COVID-19 may have in interpreting our understanding of potential safety events. Additional outcome events and subgroups may be incorporated in this study over time. Given the global scale of COVID 19 pandemic, there is an increasing need to better understand and characterize the PASC or long COVID. 9-10 This study will also aim at describing the characteristics of COVID-19 outcome/long COVID including those exposed to Paxlovid in real-world setting. Such information may inform clinical trial design and disease management for the long-term health effects of the COVID patients. Moreover, this study provides insights into understanding of potential racial disparities among patients using Paxlovid. The exploratory analyses may help identify predictors of severe COVID-19 outcomes/ manifestations and long Covid and predict the risk developing the severe outcomes/ manifestations and long Covid at individual level in real world setting.

This non-interventional study (NIS) is designated as a Post-Authorization Safety Study (PASS) and is conducted voluntarily by Pfizer.

9. RESEARCH METHODS

9.1. Study Design

This is a secondary structured population-based database cohort study with ongoing retrospective and prospective data collection utilizing electronic healthcare data in the US. This study will include adults (≥18 years of age) and pediatric patients (<18 years of age) with COVID-19 diagnosis (ie, positive polymerase chain reaction (PCR) or antigen results of direct SARS-CoV-2 viral testing or have confirmed COVID 19 diagnosis codes). All Paxlovid users will be included in the study. Within the population-based general cohort (COVID-19 Cohort), a subcohort will be created based on similar eligibility criteria as those used in select Paxlovid clinical trials (eg, C4671005, C4671002) to attempt to emulate the characteristics of select clinical trial program populations (Paxlovid Trial Similar COVID-19 Subcohorts).

9.2. Setting

This study will be conducted using Optum's COVID-19 Electronic Health Record Data during the period of January 01, 2020, to June 30, 2024. Details about the database are found in Section 9.6. The COVID-era cohorts will be refreshed annually to include additional individuals, follow-up time, and events. These refreshes and cohorts will accordingly be described in a Statistical Analysis Plan (SAP) or protocol amendment as appropriate.

9.2.1. Study Population and Cohorts

The study population will consist of patients who tested positive or were diagnosed for COVID-19 (ie, positive PCR or antigen results of direct SARS-CoV-2 viral testing or have confirmed COVID-19 diagnosis codes). All Paxlovid users will be included in the study.

Within the study population, three source cohorts of general population with COVID-19 will be formed (Figure 1):

- 1a: Overall COVID-19 patients.
- 1b: Hospitalized patients (ie, hospitalized within 30 days of index date) for COVID-19
- 1c: Non-hospitalized patients (ie, not hospitalized within 30 days of index date) with COVID-19

Within source cohort of 1a, 1b, and 1c, the following trial similar subcohorts, will be formed:

Patients at high risk of progression to severe illness (Figure 1)

- 2a: Subgroup of the general population cohort 1a who meet relevant inclusion/exclusion criteria of the Paxlovid clinical trial (C4671005).
- 2b: Subgroup of the hospitalized patient cohort 1b who meet relevant inclusion/exclusion criteria of the Paxlovid clinical trial (C4671005).
- 2c: Subgroup of the non-hospitalized patient cohort 1c who meet relevant inclusion/exclusion criteria of the Paxlovid clinical trial (C4671005).

Patients at standard risk of progression to severe illness Figure 1)

- 3a: Subgroup of the general population cohort 1a who meet relevant inclusion/exclusion criteria of the Paxlovid clinical trial (C4671002).
- 3b: Subgroup of the hospitalized patient cohort 1b who meet relevant inclusion/exclusion criteria of the Paxlovid clinical trial (C4671002).

[figure not shown]
 3c: Subgroup of the non-hospitalized patient cohort 1c who meet relevant inclusion/exclusion criteria of the Paxlovid clinical trial (C4671002).

A sub-cohort of patients who were exposed to Paxlovid in real world settings will be created.

If a patient had an exposure to paxlovid without COVID PCR/antigen testing/diagnosis data, this patient can be captured in the Paxlovid cohort.

Additional special populations (eg, immunocompromised patients, pediatric population, severe renal impairment, etc.) may be added as a subset.

A validation substudy will be a subpopulation randomly drawn from within the OPTUM EHR database. Figure 1. Flowchart Outlining the Study Cohort and Subcohorts

Note: Any addition of a special population (eg, immunocompremised patients, pediatric population, severe renal cohort etc.) as well as patients with multiple infections of COVID 19 or patients received COVID 19 vaccines can be a subset of either source cohort or high/standard risk cohort

[figure not shown]
*For Paxlovid cohort, if a patient had an exposure to paxlovid without COVID PCR testing/diagnosis data, this patient can be captured in the Paxlovid cohort.

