9.2.2.3. Index Date

The index date for the COVID-19 Source and the Trial Similar Subcohort will be defined as the date of first date tested positive or diagnosed for COVID-19 (ie, positive PCR or antigen results of direct SARS-CoV-2 viral testing or have confirmed COVID-19 diagnosis codes) during the study period.

Method to refine index date per research question will be defined in SAP.

The index date for the Paxlovid cohort will be defined as the date of first prescription of Paxlovid during the study period.

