9.2.2.4. Follow-up

The follow-up period starts at index date and participants will be followed until the date of the first occurring of the following events:

- Death;
- At the end of their database disenrollment from the database;
- At the end of study period (Section 9.2.2.1);
- Occurrence of the outcome of interest.

Follow-up time for hospitalized patients will meet the criterion in Section 9.2.1 (ie, hospitalized within 30 days of COVID 19 diagnosis or index date). Details as well as follow-up windows for long COVID will be defined in SAP.

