9.3.2.1. TSC Standard Risk Cohort and TSC High Risk Cohort

Patients meeting any of the following criteria in the TSC high risk cohort (C4671005) or TSC standard risk cohort (C4671002) will not be included in the study:

1. Females who are pregnant or breastfeeding within 9 months prior to index date.

Any time prior to index date, unless specified otherwise:

- 2. History of hospitalization within 30 days prior to Index date.
- Known medical history of active liver disease (other than nonalcoholic hepatic steatosis), including chronic or active hepatitis B or C infection, primary biliary cirrhosis, or acute liver failure.
- 4. Receiving dialysis or end stage of renal disease.

Additionally, patients meeting any of the following criteria in the TSC standard risk cohort (C4671002) will not be included in the study:

Has at least 1 characteristic or underlying medical condition associated with an increased risk of developing severe illness from COVID-19, including:

- ≥65 years of age at the index date.
- BMI≥30 kg/m².
- "High Risk Cohort Inclusion Criteria 1.c 1.1" (Section 9.3.1.1).

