9.4. Variables

Outcome events will be the pre-specified potential safety concerns, including those that were part of Paxlovid or identified after the EUA post marketing. The list of events of interest is provided below. This list of outcome events was chosen based on clinician's expert opinion, biologic plausibility, and feasibility of identification in EHR or claims data. Other potential safety concerns that arise during the post marketing, clinical trials, or based on emerging literature related to Paxlovid safety will be included in subsequent refreshes of the cohorts, or as rapid queries in response to regulatory authority requests.

Potential Safety Outcomes of Interests*

- 1. Renal impairment.
- Hepatic impairment.
- 3. Other potential safety events of interest (eg, Diarrhea, Dysgeusia, Hypersensitivity reaction/allergic reactions, and other additional potential safety events of interest may be added over time).

* The potential safety outcomes of interests listed above can be further evaluated by the covariates including (demongraphics, drug-drug interactions etc.).

Potential effectiveness of interests*

- Hospitalization;
- All-cause mortality;
- ICU/Mechanical Vitalization;
- In Hospital death.

COVID-19 complications/interventions (within 30 days of COVID 19 diagnosis):

- Pneumonia;
- Kidney failure;
- Thrombotic event;
- Acute respiratory distress syndrome (ARDS);
- HF;
- Sepsis/septic shock;
- Hospitalization;
- All-cause mortality;
- In hospital death;
- Multi-organ dysfunction/failure;
- Mechanical ventilation/ECMO (Extracorporeal membrane oxygenation).
- Vasopressor use

Time to clinical events:

- Time from index date (Section 9.2.2.3) to admission;
- Time from index date (Section 9.2.2.3) to the events above.

^{*}The outcomes may be removed to added depending on the data availability for proper analyses.

COVID-19 long term health effects:

Headache;

The following conditions may be considered for COVID-19 long term effects. This is not an exclusive list. Specific definition and follow up windows of long COVID (eg, greater than 4 weeks, 12 weeks, or 6 months after a COVID diagnosis)⁹⁻¹⁰ will be further defined in SAP.

4 weeks, 12 weeks, or 6 months after a COVID diagnosis) ⁹⁻¹⁰ will be further defined in SAP.
Abdominal pain;
Acute kidney injury;
Alopecia;
Body aches;
• Chest pain;
Cognitive impairment;
• Confusion/delirium;
Nasal congestion;
• Cough;
Anxiety disorders;

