For exploratory analysis, machine learning models (eg, LASSO Cox regression, Random Survival Forest (RSF), and XGBoosting (XGB) models) will be used to identify important predictors associated with progression to COVID-19 severe outcomes/manifestations as well as long COIVD. An ensemble method will be used to rank predictors across models and find the strongest predictors for each outcome. Patient-level prediction for the risk of developing severe outcomes/manifestation and long COVID will be performed using the top ensemble predictors. C-index and dynamic AUCs will be used to evaluate model performance. To assess the feasibility of real-world effectiveness of Paxlovid, we will apply propensity score matching (PSM) method to control confounding and PTDM to handle immortal bias. To better understand the impact of incidental hospitalization on the same date of COVID 19 diagnosis date or Paxlovid prescription date, medical note review of patients with the same date hospitalization will be conducted by OPTUM. The structured data (Hospitalization on the same date = Yes/No) will be provided by OPTUM to enable the assessment of misclassification of the hospitalization.

All data analysis will be executed using statistical software SAS version 9.4 or later.

Detailed methodology for statistical analyses in this study will be documented in a statistical analysis plan (SAP), which will be dated, filed, and maintained. The SAP may modify the plans outlined in the protocol; any major modifications of primary endpoint definitions or their analyses would be reflected in a protocol amendment.

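### Cohort 1b is labelled hospitalized for COVID-19, but its written rule is any admission within 30 days of index, and the check on incidental admissions reaches only same-date cases

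*Protocol*

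**What the plan says.** Protocol section 9.2.1 splits the overall COVID-19 cohort 1a into two parts. The first is given as "1b: Hospitalized patients (ie, hospitalized within 30 days of index date) for COVID-19". The second, which is meant to be its counterpart, is given as "1c: Non-hospitalized patients (ie, not hospitalized within 30 days of index date) with COVID-19".

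The trial-similar cohorts 2b and 3b are drawn from 1b. Section 9.2.2.4 restates the criterion, again by time alone: "hospitalized within 30 days of COVID 19 diagnosis or index date". The index date (section 9.2.2.3) is "defined as the date of first date tested positive or diagnosed for COVID-19", and symptoms are not required.

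Section 9.4 puts hospitalization, with no cause attached, under the heading "COVID-19 complications/interventions (within 30 days of COVID 19 diagnosis". It also lists time from index to admission.

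Section 9.9 shows that the sponsor has thought about incidental admission. It plans a medical note review "To better understand the impact of incidental hospitalization on the same date of COVID 19 diagnosis date or Paxlovid prescription date". The review returns a yes/no field "to enable the assessment of misclassification of the hospitalization".

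Pregnancy is an exclusion only in section 9.3.2.1, for the two trial-similar cohorts: "Females who are pregnant or breastfeeding within 9 months prior to index date". The only exclusion that applies to every cohort (section 9.3.2) concerns the gender variable.

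**The concern.** The label of 1b promises patients admitted because of COVID-19, while the rule that a programmer would implement selects patients admitted for any reason in the month after a first positive test or code. Someone who tests positive at a pre-operative screen and has the operation three weeks later meets the rule. So does a patient in source cohort 1b who tests positive late in pregnancy and delivers within the window. Both would also count towards hospitalization as a COVID-19 complication.

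Three outputs inherit the mixture: the characteristics of hospitalized patients (primary objective 1), time to hospitalization (objective 2) and the background incidence of COVID-19 complications (objective 3). Hospitalization is also on the list of potential effectiveness outcomes. The unrelated admissions form a roughly fixed floor, so their share is largest where the true COVID-19 admission risk is lowest. Section 9.11 says results should be generalizable in relation to hospitalized patients. A reader will take that to mean the patients the label describes.

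**Working it through.** **Reading the text.** The protocol states no figure on this point, so there is nothing to reproduce. The first check is whether the definitions fit together.

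1. Section 9.2.1 gives a cause in the label of 1b and only a window in the explanatory bracket. Section 9.2.2.4 repeats only the window.
2. Cohort 1c is everyone not hospitalized within 30 days, whatever the reason. Cohorts 1b and 1c together cover 1a only if 1b means any admission. If 1b were limited to admissions caused by COVID-19, a patient admitted for another reason on day 20 would be in neither.
3. No section gives an admission reason, a diagnosis position, or an exclusion of obstetric, elective or injury admissions for the source cohorts.
4. The note review in section 9.9 applies on the diagnosis or prescription date. Its stated use is to assess misclassification, and no rule moves a patient out of 1b. Other days in the window are not reviewed. The validation substudy in section 9.2.1 has no stated link to hospitalization.

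**Illustrating the size.** All inputs here are assumptions; none is in the protocol.

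- r = rate of unrelated admission, 0.06 to 0.12 per person-year
- c = 30-day risk of admission due to COVID-19: 1%, 3% or 10%
- the two kinds of admission are independent, and unrelated admissions are spread evenly over the 30 days

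30-day risk of an unrelated admission: p = 1 − exp(−r × 30/365.25).

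- r = 0.06: p = 0.49%
- r = 0.12: p = 0.98%

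Reported all-cause risk = c + p(1 − c). Incidental share of 1b = p(1 − c) / [c + p(1 − c)].

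| c | Reported risk | Incidental share |
|---|---|---|
| 10% | 10.4-10.9% | 4-8% |
| 3% | 3.5-4.0% | 14-24% |
| 1% | 1.5-2.0% | 33-49% |

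Worked line for c = 1%, r = 0.06: 0.0049 × 0.99 = 0.0049, and 0.0049 / (0.01 + 0.0049) = 33%.

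With p widened to 0.3%-2%, the share runs from 3-15% at c = 10%, through 9-39% at c = 3%, to 23-66% at c = 1%.

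The model does not represent the cluster of screening positives on the day of admission itself. It describes the background over the rest of the window, which is the part the note review does not reach.

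**The case against.** The strongest defence is textual. Cohort 1b says *for* COVID-19 where 1c says *with*, so the label could carry the cause and the bracket only the window. The protocol never writes any-cause hospitalization, and attribution by codes is ordinary SAP content. This partly stands: the SAP is not at hand and could add a cause rule. But sections 9.2.2.3 and 9.2.2.4 defer index-date refinement and follow-up details, not cohort membership. A cause rule would also break the complement between 1b and 1c.

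Four other objections limit the point:

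- **All-cause hospitalization in a fixed window is a legitimate descriptive endpoint.** This stands. The fault is the label and the missing attributed version, not the use of an all-cause count.
- **A reader might infer that deliveries contaminate 1b, 2b and 3b alike.** The text does not support that. Section 9.3.2.1 keeps most deliveries out of 2b and 3b, so that example belongs mainly to 1b. Surgery, delivery and injury are illustrations; the protocol does not name them.
- **A reader might infer that a comparison of the pre-vaccine and Omicron periods is biased.** No such comparison is planned. Section 9.2.2.1 stratifies by period, and section 9.7 calls the study descriptive and puts comparative analyses outside its scope. Only informal reading across strata is exposed.
- **The size rests on assumed rates.** This stands. The large shares need a low COVID-19 admission risk, and section 9.11 says that mild infections are under-captured, which argues against treating 1% as typical of this care-seeking population.

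It is also tempting to conclude that 1b should simply be redefined by cause. That would leave other admissions in neither cohort. It would also rely on a diagnosis code that section 9.11 dates to 01 April 2020, whereas the study period starts on 1 January 2020.

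**Conclusion.** The point holds as a mismatch between label and rule, together with an incomplete check. Taken literally, sections 9.2.1, 9.2.2.4 and 9.4 count unrelated admissions on days 1-30 as COVID-19 hospitalizations, and the review in section 9.9 neither covers those days nor reclassifies anyone. The effect falls mainly on 1b and less on 2b and 3b.

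Its size cannot be established from the protocol. At an assumed 6-12 unrelated admissions per 100 person-years it is minor where COVID-19 admission is common (4-8% of 1b at a 10% risk) and substantial where it is rare (33-49% at 1%).

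The protocol does not show that the sponsor overlooked incidental admission, that any planned comparison is invalid, or that the all-cause rule itself is wrong. The correction is worth making because it is cheap and changes what the hospitalization results can be said to show.

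**What to change.** 1. In sections 9.2.1 and 9.4, relabel 1b/2b/3b and the hospitalization endpoint as all-cause hospitalization within 30 days of index. The rule is unchanged, so 1b and 1c still partition 1a.
2. Beside it, report a COVID-19-attributed version: an admission within 30 days with a COVID-19 code as admitting or principal diagnosis, or a COVID-19 code together with a respiratory complication such as pneumonia or ARDS. Less specific complications in the section 9.4 list, such as heart failure, kidney failure or sepsis, should not qualify an admission, since they also cause ordinary admissions.
3. Show the remaining patients in 1b as a separate group, hospitalized for another reason, so that nobody drops out of the tables.
4. State in section 9.11 that the attributed version is not reliable before 01 April 2020, which is the first three of the ten months in period T1. State also that the same-date note review does not cover days 1-30.

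The cost is one derived variable from structured data already held and one extra column per table. The downside is that diagnosis position is imperfect in EHR data, so both versions should be shown and neither should replace the other.
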